3. SUMMARY OF STUDY PLAN

Eligible participants will be \geq 18 years of age and newly diagnosed pre- or post-menopausal patients with core biopsy proven invasive breast cancer between 0.5 cm and 5 cm in size or DCIS that is \geq 1.0 cm in size and is either Grade 3 ER+ DCIS or ER- DCIS of any grade

Patients agreeing to participate will take 9cUAB30 240 mg (160 mg contingent on interim analysis) by mouth daily for 14 – 28 days until the time of surgery. Tissue from the core biopsy will be used for the pre-treatment biomarker analysis. The tissue obtained from the surgical excision will be used for post-treatment biomarker analysis. We plan to enroll ER+ participants and ER- participants for a total of up to 41 participants undergoing intervention. We expect the study to be complete within 18-24 months. Beginning in November 2021, participants will be limited only to estrogen receptor negative status.

At baseline all participants will have a complete medical history, physical examination and review of concomitant medications. Participants will undergo laboratory testing to determine eligibility within 30 days prior to day 1 of the study. Baseline laboratory tests will include WBC, differential, hemoglobin,

hematocrit, platelets, INR, PTT, AST, ALT, total bilirubin, alkaline phosphatase, BUN, creatinine, calcium, glucose, albumin, electrolytes (Na, K, Co₂, Cl), HDL, LDL, total cholesterol, triglycerides, thyroid stimulating hormone, FT₃, and FT₄ (may omit any if collected as part of initial cancer workup documented in the medical record within 30 days of study Day 1). A plasma and urine sample for pharmacokinetic (PK) analysis will also be obtained. An additional 30 ml blood sample will be obtained to evaluate and measure the immune response of 9cUAB30 in participants 6-25.

For the first 5 participants, two extra plasma PK samples will be collected after administering the first dose of the study agent at 5 minutes and 2 hours post the drug administration to evaluate the C_{max}. After the first 5 participants complete study participation, their PK samples will be evaluated to determine the C_{max} and adverse events will be evaluated to determine safety of the 240mg dose. Based on this evaluation, it will be determined to continue study dose at 240mg or to reduce to 160mg (refer to section 13.9).

For all study participants, 1 H&E stained slide, 5 unstained slides of 5 μ m thickness and 5 unstained slides of 10 μ m thickness will be requested from the diagnostic core biopsy formalin fixed paraffin embedded (FFPE) tissue block containing tumor using the existing diagnostic core biopsy material already collected.

As part of the assessment of participant evalability, a pathologist will examine the deepest level cut from blocks of the core biopsy and surgical resection specimens containing tumor. If the estimated residual tumor in the block is considered sufficient to enable cutting of at least 5 unstained slides at 5 μ m thickness, needed to support the future performance of Ki-67 and caspase 3 assays, the participant can be considered evaluable.

Once a surgery date is scheduled, participants meeting eligibility requirements will begin oral 9cUAB30 for daily treatment for at least 14 (but not longer than 28 days) days at the 240 mg/day dose level (160 mg contingent on interim analysis) prior to surgery. The day the participant begins taking 9cUAB30 is considered Day 1 of the study. Each participant will be provided with a blood pressure (BP) monitor to track the BP values at home. During the visit, participants will be instructed on how to use the monitor. The instructions are noted on the BP diary (Appendix C) for reference at home. Participants will be asked to measure and document the blood pressure values in the BP diary on Day 7, Day 8 (approximately 24 hours later) and the day prior to surgery. All BP readings should be taken in the morning. They will be instructed to notify the study team if the value of the reading is Systolic \geq 160 and Diastolic \geq 100. The study coordinator will contact the participant on Day 8 by telephone to assess adverse events and other symptoms, review medications and review the BP readings. Study team will also contact participants on the day before surgery to remind them to take last dose of medication, bring the pill diary and blood pressure monitors and bring all the pill bottles given to them. Participants will be encouraged to contact the investigator or study coordinator with any new symptoms or concerns at any time during the trial.

Surgery must occur between Days 15 and 29 of the study. On the day of surgery or the day before surgery laboratory tests will be obtained and include WBC, differential, hemoglobin, hematocrit, platelets, INR, PTT, AST, ALT, total bilirubin, alkaline phosphatase, BUN, creatinine, calcium, glucose, albumin, electrolytes (Na, K, Co₂, Cl), HDL, LDL, total cholesterol, triglycerides, thyroid stimulating hormone, FT₃, FT₄, as well as a plasma and urine sample for PK. The history and physical examination will be obtained and/or updated within 24 hours of the procedure. An additional 30 ml blood sample will be obtained during this visit to evaluate and measure the immune response of 9cUAB30 by comparing it to the sample obtained at baseline for participants 6-25.

At the time of surgery, tissue samples will be obtained of remnant tumor and processed as is the usual standard at each institution. One H&E stained slide, 5 unstained slides of 5 μ m thickness and 5 unstained

slides of 10 μ m thickness will be requested from the formalin fixed paraffin embedded (FFPE) tissue blocks containing tumor as described in section 10.2.1

The plasma and urine samples for PK will be sent to University of Wisconsin - CP lab for evaluation. The immunogenicity samples will be sent to University of Washington – Tumor Vaccine Group. All other baseline and pre-surgical laboratory studies will be performed at each participating institution.

All participants will receive \$30 for completing the screening visit, \$70 for completing the surgery visit and returning the blood pressure machine as compensation towards the extra efforts taken such as travel expenses, parking, time missed from work or other expenses associated with the study visits. The first 5 participants will be given additional \$50 for the additional time required for the study visit.

The study participants will be matched with historical nonrandomized controls from each site based on sex (female), pathologic stage, receptor status, grade, and menopausal status from each site. These samples will be obtained from blocks no more than 5 years old. The pre-surgical and post-surgical tissue samples (from the participants and matched controls) will be batched and analyzed concurrently utilizing immunohistochemistry and Nanostring to measure any effects of 9cUAB30 on tumor cell proliferation (Ki67) and activation of RXR downstream pathways (gene expression). Slides will be analyzed via immunohistochemistry at Wisconsin and via Nanostring at UAB per existing protocols.

Seven days after surgery and 4-5 weeks after surgery a follow-up phone call will be performed for safety assessment.

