4.1 Inclusion Criteria

1. Female only. The sample size of males affected by breast cancer is limited, hence we will not be able to collect significant data for analysis of the effect of study drug on breast cancer in males
2. Age \geq 18 years. Because no dosing or adverse event data is currently available on the use of 9cUAB30 in participants <18 years of age.
3. ECOG performance status ≤ 1 or Karnofsky $\geq 70\%$ (convert the Karnofsky score into the ECOG scale based on Appendix A).
4. Invasive breast cancer diagnosed by needle core biopsy, between 0.5 cm and 5 cm in size based on imaging, that is ER+ or ER-, Her2neu positive or negative

OR

DCIS of the breast diagnosed by core needle biopsy and at least 1.0 cm in size based on imaging. Grade 3 ER+ DCIS will be allowed as well as ER- DCIS of any grade. For DCIS-only lesions, the imaging abnormality corresponding to the cancer must be at least 1.0 cm in size (i.e. calcifications, distortion or mass on mammogram, or mass or nonmass enhancement on MRI).

5. Participants must have normal organ and marrow function as defined below:
 - WBC $\geq 3000/\text{mm}^3$;
 - Platelets $\geq 100,000/\text{mm}^3$,

- Hemoglobin >10 g/dL;
- Bilirubin \leq upper limit of institutional normal;
- AST \leq upper limit of institutional normal
- Creatinine \leq upper limit of institutional normal
- Triglycerides \leq 1.5xULN
- Cholesterol \leq 1.5xULN

6. Participants must agree to discontinue all supplements containing vitamin A while taking study medication and for thirty days after the last dose of study medication.
7. Have not been treated with chemotherapy, or biological therapy in the last 5 years. We do not know if the previous treatment will have an effect on the tissues to be examined.
8. Have not used tamoxifen, raloxifene, or other antiestrogen compounds within 6 months of study entry. If used within 5 years of study entry, total duration of use must be less than 6 months.
9. Have not used exogenous hormone replacement therapy or hormonal contraception in the year prior to diagnosis. The use of non-systemic estrogen (such as vaginal estrogen use) is allowed.

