Additionally, each institution will provide matched samples (at the direction of UAB Pathology Core lab) from archival diagnostic core biopsy FFPE blocks containing breast cancer and archival FFPE blocks from the corresponding definitive surgical resection. Each matched case will be used to obtain 1 H&E stained slide, 5 unstained slides of 5 μ m thickness and 5 unstained slides of 10 μ m thickness from the archived core biopsy and 1 H&E stained slide, 5 unstained slides of 5 μ m thickness and 5 unstained slides of 10 μ m

thickness from the archived surgical specimen. These will be prepared and sent to Wisconsin and UAB as directed for analysis.

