10.2 Collection and Handling Procedures

The University of Wisconsin Comprehensive Cancer Center’s (UWCCC) CP Laboratory (Cancer Pharmacology Lab) will serve as the central repository for blood and urine specimens. The University of Alabama at Birmingham (UAB) Tissue Biorepository Laboratory and UWCCC TRIP will serve as the central repositories for tissue specimens. The UWCCC CP Laboratory will prepare sample kits for each

subject enrolled on the study – for both the slides being sent to UAB and UWCCC, and the blood and urine being sent to UWCCC. Each site will receive two kits as they activate the study. The CP lab will send additional kits to the sites as needed based on the rate of accrual.

Each kit will be sent in a box to each site. Each box will contain:

- Styrofoam cooler for blood and urine samples and airbill – which go to UWCCC
- Slide mailers, shipping box and airbill for slides – which go to UWCCC and UAB

The University of Washington will ship 2 kits for the 30 mL peripheral blood to each of the sites prior to start of the trial and then will ship further kits to the sites as needed based on recruitment. The University of Washington will train the sites on packing and shipping the blood. All blood processing and storage during the trial will be performed at the University of Washington and after analysis any remaining specimens will be returned to the Division of Cancer Prevention repository.

10.2.1 Methods for preparing tissue specimens of participants and historical matched controls.

NOTE:

- Unstained sections are to be mounted on charged slides
- Historical matched samples should be prepared at the same time as the participant tissue sample.

From both the participant's and historical matched sample of pre-surgical core biopsy and the definitive surgical resection:

- A pathologist should identify, from each procedure, a FFPE archival block that contains an adequate amount of malignant tumor tissue to support the preparation of 11 slides (1 H&E stained slide, 5 unstained slides of 5 μ m thickness and 5 unstained slides of 10 μ m). If the core biopsy will not support the preparation of 11 slides, 1 H&E stained slide, and 5 unstained slides at 5 μ m will be acceptable.
- Samples that are considered adequate and eligible for analysis:
 - From the core biopsy – contain >20% malignant nuclei
 - From the surgical tumor sample – contain >10% malignant nuclei

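### Controls are matched on pathologic stage and on grade from an unnamed specimen, not on core-biopsy lesion type; the matching factors should be fixed on pre-treatment data

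*Combined protocol and SAP*

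**What the plan says.** Section 3 (Summary of Study Plan) states that participants are "matched with historical nonrandomized controls from each site based on sex (female), pathologic stage, receptor status, grade, and menopausal status", using blocks no more than five years old. It does not say whether stage, grade and receptor status come from the core biopsy or the resection, or when the match is fixed.

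Entry rests on pre-treatment information. Section 4.1 admits "Invasive breast cancer diagnosed by needle core biopsy, between 0.5 cm and 5 cm in size based on imaging", or "DCIS of the breast diagnosed by core needle biopsy and at least 1.0 cm in size based on imaging". Lesion type comes from the core and size from imaging.

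The resection comes after the drug. Section 3: "Surgery must occur between Days 15 and 29 of the study".

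On control tissue, Section 10.2.1 says: "Historical matched samples should be prepared at the same time as the participant tissue sample". Section 9.1 places the choice of matched samples under the pathology core laboratory's direction and gives no algorithm or tolerance. For each procedure, Section 10.2.1 asks the pathologist for "a FFPE archival block that contains an adequate amount of malignant tumor tissue", with more than 20% malignant nuclei in the core and more than 10% in the surgical sample. It does not ask for the same component, in situ or invasive, at both times.

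Sections 13.1 and 13.4 make the treated-control pair the unit of the primary analysis: a one-tailed paired test at 0.05 on the difference in absolute Ki67 change.

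**The concern.** There are two separate problems.

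**Post-treatment matching.** The agent is hypothesised to reduce proliferation and increase apoptosis. If a matching factor is read from the resection and moves with surgical Ki67, the control is chosen to resemble the treated tumour after the drug has acted. Controls with low surgical Ki67 are then over-selected, and part of a real effect is matched away.

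**Lesion type at baseline.** A participant with DCIS on core and invasive cancer at resection carries an invasive pathologic stage. The rule allows a control who was invasive at both times. Her Ki67 change then runs from DCIS to invasive, and her control's from invasive to invasive. This can happen even if the drug does nothing.

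Section 13.1 introduces the control group to account for variability associated with the core biopsy. Both problems weaken it for that purpose, in a trial that expects about 28 evaluable pairs.

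**Working it through.** **1. The plan's own figures (Section 13.3).** SD of the paired difference with pair correlation 0: √(57.5² + 14.8²) = 59.4. Effect sizes: 29.8/59.4 = 0.502 and 44.6/59.4 = 0.751. One-sided paired t-test at 0.05 with 28 pairs, by the noncentral t: power 0.827 and 0.987, against 0.82 and 0.98 in the plan's table. The table reproduces. Because the plan takes the pair correlation as 0, its power already gives no credit for good matching.

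**2. Matching on a surgical-specimen factor (illustration; every input is an assumption).** Median Ki67 22%, between-tumour log-SD 0.6, measurement log-SD 0.20 to 0.35, and a three-level matching stratum that tracks log Ki67 with noise 0.3 to 1.0. Control changes are reweighted to the treated distribution of the stratum. Contrasts are in Ki67 points.

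| True fall | True contrast | Core stratum | Surgical stratum tracking *measured* surgical Ki67 | Surgical stratum tracking the *underlying* tumour |
|---|---|---|---|---|
| None | 0 | about 0 | about 0 | about 0 |
| 30% | −8.1 to −8.4 | unchanged | −7.05 to −7.86 | unchanged |
| 45% | −12.1 to −12.6 | unchanged | −10.6 to −11.8 | unchanged |

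Smallest and largest losses at a 30% fall: 8.07 − 7.86 = 0.21 points (3%) and 8.39 − 7.05 = 1.34 points (16%). At 45% they are about 0.3 and 2.0 points, again 3% to 16%.

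The loss depends on what the stratum tracks. It appears when the stratum shares the measured value, including sampling and assay error, of the surgical slide. It disappears when the stratum tracks only the underlying tumour. When tumours were also allowed to change at random between core and surgery without drug (log-SD 0.20), it returned in the same direction, within the range above.

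**3. Consequence for power at 28 pairs.** The shrinkage is applied as a proportion to the planned differences.

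- 29.8 × 0.97 = 28.9, effect size 0.487, power 0.81.
- 29.8 × 0.84 = 25.0, effect size 0.421, power 0.70.
- 44.6 × 0.84 = 37.5, effect size 0.631, power 0.95.

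**4. DCIS upgraded to invasive.** Let p_T and p_C be the shares of treated and control members with a DCIS core and an invasive resection. Let δ be the difference in expected Ki67 change between DCIS-to-invasive and invasive-to-invasive cases. The shift in the mean contrast is (p_T − p_C) × δ.

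- If, within stage, core DCIS is as common in the archive as among participants, p_T = p_C in expectation. The shift is 0 and only noise remains.
- Extreme case, with p_T = 2/28, p_C = 0 and δ of 5 to 15 points (all assumed): 2/28 × 5 = 0.36 and 2/28 × 15 = 1.07 points. The direction follows the sign of δ, which the documents do not give.

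**5. Cost of excluding discordant pairs in a sensitivity analysis.** At effect size 0.502, power goes from 0.827 with 28 pairs to 0.815 with one dropped, 0.801 with two and 0.737 with six.

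**The case against.** The strongest counter-case is that the shrinkage needs an assumption that does not suit stage. The simulated stratum correlates with log Ki67 at roughly 0.51 to 0.89 (0.6/√(0.6² + noise²), noise 1.0 and 0.3). Nothing in the documents supports that for pathologic stage, links stage to Ki67 measurement error, or shows that 14 to 28 days of drug alters stage. With stratum noise of 2.0, the loss at a 30% fall is only about 0.07 to 0.2 points. This stands. Grade read from the surgical specimen is the more plausible route, and the plan does not say which grade is used.

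The documents also never state that stage is taken from the resection; that follows from the ordinary meaning of the term. Controls have a core and a resection too, so an upgraded participant might receive an upgraded control. A reader might infer that the rule necessarily mispairs such women. It does not: it neither requires nor prevents the mismatch, and no upgrade rate is given.

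Matching on core lesion type can move the mismatch to surgery, since a DCIS-core control will often be DCIS at both times. That is true of single pairs. Fixing the baseline balances lesion type before treatment and leaves upgrading to balance on average. Same-component scoring addresses the pair itself, where that component remains.

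Finally, immunohistochemistry follows laboratory protocols that are not reproduced here. A component rule may exist there. If so, it should be cited.

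**Conclusion.** The point holds as a weakness in the matching rule. As written, the rule can condition on a post-treatment result, and it need not balance lesion type at baseline in the pairs that the primary test uses.

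Its size cannot be derived from the documents. Under the stated assumptions, a surgical-specimen factor that shares measured surgical Ki67 costs 3% to 16% of a real effect; a factor that tracks only the underlying tumour costs nothing. Stage probably lies near the bottom of that range or below it, and surgical grade could lie higher. DCIS upgrading shifts the mean by about 0.4 to 1.1 points in the extreme case shown, and otherwise adds noise.

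A reader might infer an inflated false-positive rate. For matching on surgical stage or grade, the documents and the calculation do not support this: with no drug effect the contrast was unbiased. DCIS pairs could bias in either direction, but only if the core DCIS mix differs between participants and archive, and the documents do not address that. The planned sample size and the stated power need no change.

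**What to change.** **Section 3.** Replace pathologic stage and unspecified grade with pre-treatment factors: core-biopsy lesion type (DCIS-only or invasive), core-biopsy grade, core-biopsy receptor status, and imaging size category where archived. Leave menopausal status and site unchanged.

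**Section 10.2.1.** Require Ki67 and caspase 3 to be scored in the same component, in situ or invasive, in core and surgical sections wherever that component is present in both.

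**Section 13.4.** Add a sensitivity analysis that excludes pairs in which either member's core and surgical histology differ. Report how many there are in each group, which also shows whether the core DCIS mix is similar.

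**Controls already selected.** Do not replace them. Check their core-biopsy data and report concordance with the participant on the new factors.

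**Cost.** No extra participants or samples. Core lesion type, imaging size and receptor status are established for participants at eligibility. Core grade is explicitly needed only for ER-positive DCIS, but should be in the pathology reports that Section 10.3.1 sends with the slides. The archived core data must be checked, and the documents do not show how complete they are. Imaging size is less exact than pathologic size, and requiring it would narrow a pool already limited by site and block age; hence its use only where archived.

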7.3 Evaluation During Study Intervention

7.3.1 Day 1

Participant starts study medication. This day will be determined based on when the surgery will be scheduled for the participant. The study drug should be started at minimum 14 days before scheduled surgery and not more than 28 days before surgery. In order to avoid any further delay of surgery due to participation in the study, it will be recommended that the study medication be started as soon as the participant is deemed eligible. For the first 5 participants this will be in clinic on the day of screening visit.

7.3.2 Day 7

Home BP monitoring in the morning. They will note the BP value and time reading taken in the BP diary and call the study team if they see a value of systolic \geq 160 or diastolic \geq 100. Participants will be instructed to repeat the reading after 5 minutes if the value of the reading is Systolic \geq 120 or Diastolic \geq 80. The average reading of the two measurements will be noted in the database and used for adverse event determination. See section 11.1.1 Reportable AEs, for how the blood pressure should be obtained.

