9. CORRELATIVE/SPECIAL STUDIES

9.1 Rationale for Methodology Selection

The primary goal of the study is to ensure that 9cUAB30 produces a biological effect in humans to justify pursuing more large-scale studies of 9cUAB30. To assess response to 9cUAB30, expression levels of biomarkers will be assessed pre and post treatment with immunohistochemistry (IHC) and Nanostring technology. We have incorporated a nonrandomized matched “control” cohort to better understand baseline variability in biomarker analysis between diagnostic core biopsy and surgical resections.

If the treatment agent 9cUAB30 is effective against breast cancer, it should reduce proliferation and/or kill breast cancer cells. In paraffin blocks, proliferation is assessed by immunohistochemistry via measuring changes in Ki67 and cell death is measured by the caspase 3 assay and routine histology. Another measure of proliferation is PCNA. However, all cells of breast cancer frequently stain with PCNA so it is not very useful. Paraffin embedded biopsy tissue will be compared with paraffin embedded tissue after definitive surgery following treatment with 9cUAB30. These assays will be performed on 5 μ m tissue sections from paraffin embedded tissues. Prior to analyzing treated cases, there will be a study of the variability of Ki67 and caspase 3 between biopsies and definitive surgery (i.e., excision of any remaining tumor either in a lumpectomy or in a mastectomy). This study will be performed on retrospective samples which have not been treated between the biopsy and definitive surgery from each institution. Other than this, there will be no existing data with which to compare results of treatment with 9cUAB30 in this format of analysis.

Specifically, at each institution, pretreatment core biopsy FFPE blocks containing breast cancer will be used to obtain 5 unstained slides of 5 μ m thickness for immunohistochemistry analysis to be performed at Wisconsin and 1 H&E stained slide, 5 unstained slides of 10 μ m thickness for Nanostring analysis to be performed at UAB. Post treatment, 1 H&E stained slide, 5 unstained slides of 5 μ m thickness and 5 unstained slides of 10 μ m thickness will be prepared from diagnostic FFPE blocks from the definitive surgical resection for analysis also to be performed at Wisconsin and UAB.

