This is a single arm open label pre-surgical “window trial” of the novel rexinoid 9cUAB30. The primary objective is to evaluate whether therapy with 9cUAB30 substantially reduces proliferation in breast cancer cells. To test the hypothesis that proliferation decreases in 9cUAB30 treated cases, we plan to examine Ki67 from newly diagnosed breast cancer patients. For each enrolled participant, we will obtain baseline core biopsy tissue samples and post-treatment definitive surgical tissue samples. To account for potential confounding variability associated within the tumor as a result of core biopsy, we plan to include a matched historical nonrandomized “control” group which will have an initial sample as well as post-surgical sample. This matched group will come from archived tissue samples of core biopsy and definitive surgical tissue samples available at each participating Institution. The primary endpoint will be the absolute change in Ki67 expression in each treated participant and matched “control” pair.

The primary analysis will compare the difference in absolute change in Ki67 between treatment and matched “control” group using a one-tailed paired t-test or Wilcoxon signed-rank test, as appropriate, at a significance level of 0.05. We chose the one-tailed test as we are only interested in detecting the reduction in Ki67 expression level with 9cUAB30 as compared to controls.

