13.3 Accrual and Feasibility

According to Dowsett et al., there was a mean decrease in Ki67 of 59.5% and an estimated standard deviation (SD) of 57.5% with tamoxifen, the least effective among tamoxifen alone, anastrozole alone, and tamoxifen/anastrozole combination.³⁴ As we do not know if 9cUAB30 will have as much of a decrease as tamoxifen, we will use a range of more conservative estimates, from 50-75% of 59.5%, or 29.8-44.6%. According to Chen et al., there was a mean increase in Ki67 of 1.7% with a SD of 7.6% based on three untreated observations with the time interval comparable to the proposed study.⁴³ However, three observations for estimation of SD is not reliable. Instead we used the widest interval-based SD estimate of 14.8% (from the 2-4 day interval), to be conservative. We also conservatively used an estimate of 0% for change in the control group instead of 1.7%, again, because of the sample size consideration.

Since we are using matched pairs, we needed to estimate the mean and SD of the difference between the matched pair. With 0% as our control estimate, the estimate of the range of the mean difference is thus 29.8-44.6%. The SD is estimated using the equation $\sqrt{\sigma_T^2 + \sigma_C^2 - 2\rho\sigma_T\sigma_C}$ where σ_T is the SD of the treatment group, σ_C is the SD of the control group, and ρ is the correlation between the matched pair. The value of this equation increases as ρ decreases in value, so an estimate using a smaller correlation coefficient is more conservative. This correlation is unlikely to be negative. Also, if the effect on Ki67 is not dependent on the factors that will be used to choose the matched controls, the correlation is likely to be close to 0. For these reasons, we use 0 as the estimate of ρ ; this gives an estimate of 59.4% for the SD of the difference between the matched pair.

We will enroll 36 participants, and obtain 36 matched pairs. Stratified analyses will be conducted if we reach a minimum of 12 participants (and matched pairs) with ER-. Assuming 20% of the participants cannot be evaluated at the end of study due to dropout or unevaluable/unavailable specimen, we will have approximately 28 participants, with 9 participants with ER- and 19 with ER+. The range of mean difference

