13.4 Primary Objective, Endpoint(s), Analysis Plan

The primary objective will be to evaluate if there is a significant decrease in proliferation (Ki67) expression in breast cancer cells from baseline to post-exposure in participants treated with 9cUAB30 compared with matched controls. The primary endpoint is the absolute change from baseline to post-exposure in 9cUAB30 treated and matched controls in Ki-67 in breast epithelial cells obtained by needle core biopsy. The baseline, post-exposure, absolute change in Ki-67, and difference in absolute change between the treated and matched controls will all be summarized with descriptive statistics. The primary analysis will compare the absolute change in Ki-67 between treatment and matched “control” group using a one-tailed paired t-test or Wilcoxon signed-rank test, as appropriate, at a significance level of 0.05.

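### Historical controls are not chosen on core-biopsy-to-surgery interval and the primary paired test does not address it, leaving an avoidable possible bias of unknown size and direction in the Ki67 contrast

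*Combined protocol and SAP*

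**What the plan says.** Section 3 (Summary of Study Plan) matches controls "based on sex (female), pathologic stage, receptor status, grade, and menopausal status from each site". The only time rule for controls is the 5-year limit on block age, which is a different quantity from the time between biopsy and surgery.

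Section 13.1 gives their purpose: "To account for potential confounding variability associated within the tumor as a result of core biopsy, we plan to include a matched historical nonrandomized" comparison group, with an initial and a surgical sample for each case. Section 13.4 then compares treated and control change in Ki67 by a "one-tailed paired t-test or Wilcoxon signed-rank test, as appropriate, at a significance level of 0.05". No covariate, restriction or sensitivity analysis for interval is given.

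For treated participants, Section 7.3.1 says: "The study drug should be started at minimum 14 days before scheduled surgery and not more than 28 days before surgery". Section 3 accordingly places surgery on Days 15 to 29.

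Two parts of Section 9.1 come close to the point. One states: "Prior to analyzing treated cases, there will be a study of the variability of Ki67 and caspase 3 between biopsies and definitive surgery", using untreated archival cases. The other puts the supply of matched samples under the direction of a core pathology laboratory. Neither contains an interval rule or a link to the primary test.

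**The concern.** The primary estimate is treated change minus control change, so the control change has to stand for what would have happened to the treated tumours without drug over the same period. A participant on schedule cannot have surgery less than 14 days after Day 1, and her biopsy came before that. A patient operated on a few days after biopsy could not have completed the trial as planned, yet nothing stops her from serving as a control.

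If the intervals differ systematically and Ki67 change after biopsy varies with interval, the interval effect is counted as drug effect, in either direction. The plan treats interval as relevant elsewhere: Section 13.3 cites an untreated figure "based on three untreated observations with the time interval comparable to the proposed study" and labels its control SD by interval. The title of the source on Ki67 change after core biopsy in the reference list says that surgery time interval may have an influence. Interval was thus considered when looking for planning data, but not when setting the rule for choosing controls.

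**Working it through.** **1. Is interval covered anywhere?** The places that govern the controls, side by side:

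- Section 3: six matching factors including site, plus block age; no interval.
- Section 8.2 (immune profiling): external comparator tumours matched by site; no interval.
- Section 9.1: variability study and core-laboratory direction; no interval.
- Section 10.2.1: slide preparation and tumour-content thresholds; no interval.
- Sections 13.1 and 13.4: paired test; no interval.

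**2. Which intervals are possible?** Treated: (biopsy to Day 1) + at least 14 days. Control: any length. The asymmetry lies in the rules; the documents do not give the intervals actually observed.

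**3. Reproducing the plan's power.** Inputs from Section 13.3: treated SD 57.5, control SD 14.8, correlation 0, mean difference 29.8 to 44.6, 28 evaluable pairs, one-sided 0.05.

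- SD of the paired difference = √(57.5² + 14.8²) = 59.4.
- Effect sizes: 29.8/59.4 = 0.502 and 44.6/59.4 = 0.751.
- Power from the noncentral t distribution, 27 df, noncentrality = effect size × √28: 0.827, 0.943 and 0.987 at 0.502, 0.626 and 0.751. The plan's table has 0.82, 0.94 and 0.98, so it reproduces. (The text of Section 13.3 attaches 0.82–0.98 to 32 participants; the values belong to 28.)

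**4. What an interval bias would do.** Let b be a bias in the paired contrast. The documents give no size for b, so every value is an assumption. Noncentrality = (effect ± b)/59.4 × √28. For example, b = 5 with no drug effect gives 5/59.4 × 5.292 = 0.445.

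| Assumed b | One-sided error, b towards drug | Power at 29.8, b against drug | Power at 44.6, b against drug |
|---|---|---|---|
| 0 | 0.050 | 0.827 | 0.987 |
| 1.7 | 0.067 | 0.787 | 0.981 |
| 3 | 0.083 | 0.752 | 0.975 |
| 5 | 0.113 | 0.694 | 0.963 |

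The 1.7 is borrowed as a size from the plan's untreated mean change. It is not an estimate of an interval effect. It rests on three observations with SD 7.6, and its 95% confidence interval is 1.7 ± 4.303 × 7.6/√3 = 1.7 ± 18.9, or about −17 to +21.

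**5. Dependence on the SD.** The 59.4 comes mainly from a percentage decrease under tamoxifen, while the endpoint is absolute change. With an assumed SD of √2 × 14.8 = 20.9, biases of 1.7 and 5 points give one-sided errors of 0.11 and 0.34.

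**6. Would regression adjustment solve it?** One could regress the within-pair difference in Ki67 change on the within-pair interval difference and read the intercept as an adjusted effect. But a treated participant's interval includes her time on drug. Illustration, all assumed: effect 29.8 at 21 days and proportional to duration (29.8/21 = 1.42 per day); duration uniform over 14–28 days (variance 14²/12 = 16.3); pre-dose SD 7 days (variance 49); control-interval SD 5 to 10 days (variance 25 to 100); mean mismatch 14 days.

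- Spurious slope = 1.42 × 16.3 / (16.3 + 49 + 25 to 100) = 0.26 to 0.14 per day.
- Real effect removed from the intercept = 14 × slope = 3.6 to 2.0 points.

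That is of the same order as the biases in step 4, so the intercept is not a safe adjusted estimate.

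**The case against.** The strongest reply is that no bias is shown. This is right: the documents establish neither that intervals differ between groups nor that Ki67 change depends on interval, and a reader who infers that the primary result is biased goes beyond them.

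Mismatch is also less likely than the 14-day floor suggests. Section 3 starts drug once a surgery date is set, Section 7.3.1 recommends starting as soon as the participant is eligible so that surgery is not further delayed, and controls come from the same site. This mitigates the concern, but the floor remains for one group only.

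Section 13.3 should not be over-read either. It cites the comparable-interval figures but plans with neither: it takes the SD from the 2–4 day interval and sets the control change to 0%. Section 9.1 also gives the controls a wider purpose, understanding variability between core biopsy and resection, part of which need not depend on interval. Both points stand. They weaken any charge of inconsistency, but do not supply an interval rule.

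A reader might also infer that biopsy and surgery dates are not captured. That cannot be concluded, because the case report forms and laboratory manual are not among the documents. What can be said is that no interval analysis is stated, so a later one would be post hoc.

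Finally, every added matching factor competes with the others. That argues for a preference among eligible controls rather than a strict criterion.

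**Conclusion.** The point holds as a design weakness worth considering: a possible bias, avoidable at low cost, of unknown size and direction. It rests on the absence of any interval rule for controls, the floor of at least 14 days for treated participants, and a primary test that takes the pairs as they come.

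The error-rate figures are illustrations and support neither a claim that the effect is small nor that it is material. At the plan's SD of 59.4, assumed biases of 1.7 to 5 points move the one-sided error to between 0.067 and 0.113 and hardly affect power at the top of the planned range. At an assumed SD of 20.9, 1.7 and 5 points give 0.11 and 0.34. Sample size and planned power are not in question.

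**What to change.** 1. **Section 3.** For pairs not yet selected, choose among otherwise eligible controls the one closest to the participant in core-biopsy-to-surgery interval, without knowledge of Ki67. State it as a preference, so that no pair is dropped.
2. **Section 13.4.** Prespecify that the interval is reported by group and as a within-pair difference for all pairs, including those already selected, using biopsy and surgery dates from pathology records.
3. **Leave the primary test unchanged.** Do not present a regression intercept as an adjusted drug effect, since it can remove real effect. If a supportive check is wanted, prespecify either repeating the primary test in pairs whose intervals are close, with closeness defined in advance, or examining Ki67 change against interval in the untreated controls only.

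The cost is two dates per case and a somewhat narrower choice of control; how much narrower is unknown because archive sizes are not given. Reach is limited. This is Version 20, and Section 10.2.1 says: "Historical matched samples should be prepared at the same time as the participant tissue sample". Pairs already chosen can therefore benefit only from the reporting and the supportive check. A preference without a fixed limit also cannot guarantee close intervals, so the reported distribution is what will let readers judge comparability.
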